3.10.4 Potential Covariates and/or Subgroups

As an exploratory analysis, appropriate univariate statistics will be used to identify potential confounders for inclusion in multivariable regression models for assessment of the primary endpoint. The following covariates will be considered:

- Patient with acute coronary syndromes (defined as any previous diagnosis of unstable angina, NSTEMI or STEMI)
- STEMI > 48 hours
- Stable angina
- Baseline troponin (positive vs. negative)
- Planned PCI access (femoral vs. radial)
- Number of stents implanted
- Number of vessels treated (multivessel vs. single vessel)
- Total infusion time
- Patients receiving P2Y12 antagonist therapy between 24 and 6 hours prior to randomization
- Patients receiving P2Y12 antagonist therapy between 6 and 1 hours prior to randomization
- Patients receiving P2Y12 antagonist therapy between 1 hour prior to randomization and 15 minutes after completion of the PCI procedure
- Type 2 diabetes mellitus
- Age < 65 years, ≥ 65-74 years and ≥ 75 years
- Sex
- Clopidogrel
- Prasugrel
- Ticagrelor
- Indication for PCI (Urgent vs. Elective)

RESPONSIVE
RELIABLE
RESULTS

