9.6 Planned Methods of Analysis

General Principles

For continuous variables, descriptive statistics (mean, SD, median, and quartiles) will be tabulated by treatment group. For categorical variables, the number and proportion of patients in each category will be tabulated.

The primary and secondary endpoints will be analyzed using the MITT population. Safety endpoints will be analyzed using the safety population. Demographics, baseline characteristics, and other study assessments will be analyzed using the MITT and intent-to-treat (ITT) population.

Confidence intervals will be used to assess hypotheses of non-inferiority and superiority. Details of the statistical methods will be developed in the Statistical Analysis Plan (SAP).

Demography and Baseline Characteristics

All appropriate background data will be summarized for each treatment group. If there are heterogeneities between two groups in any of the patient characteristics that are of clinical importance or could affect the study outcome, the impact of the imbalances will be investigated. If necessary, adjustments may be made in the efficacy and safety analysis and will be documented in the study report.

Primary Endpoint

The first primary and co-primary endpoints will be analyzed by the use of a one-sided 97.5% confidence interval

Subgroup/Covariate Analyses

Formal subgroup analyses will be performed by including the appropriate interaction terms in multivariable logistic regression models. The effects of potential covariates (see Section 9.3.4) will be assessed using multi-variable logistic regression.

Secondary Endpoints

The analysis of the secondary endpoints will be conducted in the same way as for the primary endpoint.

Safety Endpoints

The analysis of these safety endpoints will compare the incidence in the short tirofiban treatment group to the incidence in the eptifibatide group, the incidence in the short tirofiban treatment group to the incidence in the long tirofiban treatment group and the incidence in the long tirofiban treatment group to the incidence in the eptifibatide group, using the Fisher's mid-p (Berry and Armitage, 1995). Serious adverse events will also be tabulated overall and by severity for each treatment group.

Multiplicity (Multiple Endpoints)

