3 STATISTICAL METHODS

3.1 Statistical Handling Policy

3.1.1 Analysis Conventions

This section details general guidelines to be used for the statistical analyses. Deviations from these general policies may be given in the specific detailed sections of this statistical analysis plan. When this situation occurs, the rules set forth in the specific section take precedence over the general conventions. The following policies will be applied to all data presentations and analyses:

- Two-tailed tests will be performed for analyses that use statistical testing with a significance level of $\alpha = 0.05$. One-tailed tests will be performed for analyses with a significance level of $\alpha = 0.025$, if applicable.
- Summary descriptive statistics will consist of the number and percentage of responses in each category for discrete variables, and the mean, median, standard deviation (SD), minimum, maximum, and 95% confidence interval for continuous variables.
- All mean and median values will be formatted to one decimal place. Standard deviation values will be formatted to two decimal places.
- All percentages will be rounded to one decimal place. Where appropriate, the number and percentage of responses will be presented in the form XX (XX.X %), where the percentage is in the parentheses.
- For any analysis output, estimates and their corresponding standard deviations and/or standard errors will be reported up to the 3rd or 4th decimal place, per the default output of SAS.
- All p-values will be rounded to 4 decimal places (SAS format p-value). All p-values that round to 0.000 will be presented as '<0.001' and p-values that round to 1.000 will be presented as '>0.999'. Any p-value ≤ 0.05 will be considered statistically significant.
- All listings will be sorted for presentation in order of treatment group, site number, subject number, and date of procedure or event, when applicable.

- When necessary for analysis purposes, partial dates will be imputed (i.e., turned into complete dates) using the most conservative approach.
- Where appropriate, all analyses and summary tables will have the population sample size for each treatment group in the column heading.
- Tables will include titles with the corresponding analysis population and footnotes describing the analyses involved, and listings of covariates included in the analyses, where relevant.
- Version 20.0 (or higher) of MedDRA will be used for adverse event and pre-treatment conditions coding.

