3.10 Analysis of the Study Endpoints

3.10.1 Analysis of the Primary Endpoint

To evaluate the effectiveness of tirofiban versus eptifibatide, we look at the proportion of patients with at least one of the following endpoint measurements: death, PPM, uTVR or REPLACE-2 Major bleeding within 48 hours following PCI or hospital discharge, whichever comes first. For each pairwise comparison:

- The short tirofiban group is non-inferior to the eptifibatide group;
- The short tirofiban group is non-inferior to the long tirofiban group;
- The long tirofiban group is non-inferior to the eptifibatide group;

The following hypothesis will be tested:

$$H_0: C - T \leq -0.191$$

$$H_1: C - T > -0.191$$

To test this hypothesis, the difference ($C - T$) and its associated one-sided 97.5% confidence interval will be calculated. If the lower bound of the interval is greater than -0.191, the non-inferiority will be claimed. In order to compute the risk (proportion) difference for data with binary

response (“Yes” vs. “No”), a bivariate logistic regression will be performed for each pairwise comparison with the following specifications:

- The dependent variable will be “composite endpoint” and the independent factor will be “treatment group”;
- The risk (proportion) difference between two methods as well as its confidence interval will be estimated;
- The non-inferiority margin is 19.1%

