Note: This table will also be repeated for Per-Protocol Population.

Table 15 (a) Multivariate Logistic Regression Models for Primary Outcome – mITT Population

Parameter	Level	Estimate	Standard Error (SE)	Odds Ratio (OR)	95% CI for OR	Risk (Proportion Difference)	Standard Error (SE) of Risk Difference	95% CI for Risk Difference	p-value *
Primary composite outcome	Short Tirofiban vs. Eptifibatide								
Primary composite outcome	Short Tirofiban vs. Long Tirofiban								
Primary composite outcome	Long Tirofiban vs. Eptifibatide								

* p-value is the overall p-value from the logistic regression model.

Note: The following potential covariates, as well as all significant 2-way interaction terms, will be assessed using appropriate univariate statistics for consideration in the multivariate regression models:

- *Patient with acute coronary syndrome*
- *STEMI > 48 hours*
- *Stable angina*
- *Baseline troponin (positive vs. negative)*
- *Planned PCI access (femoral vs. radial)*
- *Number of stents implanted*
- *Number of vessels treated (multivessel vs. single vessel)*
- *Total infusion time*
- *Patients receiving P2Y12 antagonist therapy between 24 and 6 hours prior to randomization*
- *Patients receiving P2Y12 antagonist therapy between 6 and 1 hours prior to randomization*
- *Patients receiving P2Y12 antagonist therapy between 1 hour prior to randomization and 15 minutes after completion of the PCI procedure*
- *Type 2 diabetes mellitus*
- *Age < 65 years, ≥ 65- 74 years and ≥ 75 years*

- *Sex*
- *Clopidogrel*
- *Prasugrel*
- *Ticagrelor*
- *Indication for PCI (Urgent vs. Elective)*

Note: This table will also be repeated for Per-Protocol Population.

Table 16. Descriptive Statistics of Secondary Outcomes by Treatment Group – mITT Population

Parameter	Treatment Group		
	Short Tirofiban (N=)	Short Tirofiban (N=)	Short Tirofiban (N=)
Secondary outcome 1, n (%)			
Yes			
No			
Secondary outcome 2, n (%)			
Yes			
No			
Secondary outcome 3, n (%)			
Yes			
No			
Secondary outcome 4, n (%)			
Yes			
No			
Secondary outcome 5, n (%)			
Yes			
No			
Secondary outcome 6, n (%)			
Yes			
No			
Secondary outcome 7, n (%)			
Yes			
No			

Parameter	Treatment Group		
	Short Tirofiban (N=)	Short Tirofiban (N=)	Short Tirofiban (N=)
Secondary outcome 8, n (%)			
Yes			
No			

Note: The definitions of secondary outcomes are:

- *Secondary outcome 1: death, PPM or uTVR within 48 hours following PCI or hospital discharge, whichever comes first*

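### The exploratory adjusted model of the primary endpoint is picked by an unspecified screen whose candidates include post-randomisation variables, one of them largely set by treatment arm

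*SAP*

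**What the plan says.** SAP 3.10.1 sets the decision analysis: "a bivariate logistic regression will be performed for each pairwise comparison", with treatment group as the only factor. The one-sided 97.5% bound of the risk difference is compared with -0.191.

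SAP 3.10.4 then describes a second model, which it labels exploratory: "appropriate univariate statistics will be used to identify potential confounders for inclusion in multivariable regression models". Its 18 bullets (my count) include "Baseline troponin (positive vs. negative"), planned access, urgent or elective indication, number of stents implanted, number of vessels treated, total infusion time, and P2Y12 therapy in a window that ends 15 minutes after PCI.

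The note to mock Table 15(a) in SAP section 6 repeats the list and adds two-way interactions: "as well as all significant 2-way interaction terms, will be assessed using appropriate univariate statistics for consideration in the multivariate regression models". The table prints an adjusted risk difference, standard error and 95% CI for each of the three comparisons, and is repeated for the per-protocol population.

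No threshold is given for the screen. The only general convention is in SAP 3.1.1: "Any p-value ≤ 0.05 will be considered statistically significant". Randomisation is stratified by femoral or radial access (SAP 2.8), but access is fixed in neither model. Protocol 9.6 adds, after discussing baseline imbalance: "If necessary, adjustments may be made in the efficacy and safety analysis and will be documented in the study report". That sentence has no defined trigger, names no covariates and does not carry the exploratory label.

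**The concern.** In a randomised comparison, covariates are best fixed in advance because they are expected to predict outcome or were used to stratify. Here they are chosen from the outcome data of an open-label trial by a rule that two statisticians could apply differently. Three comparisons in two populations give 3 x 2 = 6 places where the model could be selected, and nothing says that the covariate set is common to them. The printed standard error treats the chosen model as if it had been fixed. If a treatment-by-covariate term enters, the treatment coefficient is no longer an overall effect, and the SAP does not say how the printed risk difference would be averaged.

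The list also mixes baseline variables with variables that arise after randomisation. Adjusting for something that the allocated treatment determines removes part of the effect being estimated, and where it nearly duplicates the arm it leaves little information to estimate that effect.

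At stake is the only adjusted estimate of the primary endpoint that the SAP tabulates. A reader will set it beside the confirmatory result.

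**Working it through.** **1. The plan's own sample size.** Inputs (SAP 2.6 and 3.10.1): event rate 0.51 in both arms, margin 0.191, one-sided alpha 0.025, power 99%. I take 1:1 allocation and unpooled variance.

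n per arm = (1.960 + 2.326)² x 2 x 0.51 x 0.49 / 0.191² = 251.7, so 252 per arm and 504 in total. The plan says about 500. Power at 500 is 98.96%, so the figure reproduces. The unadjusted standard error at 250 per arm is √(2 x 0.51 x 0.49 / 250) = 0.0447.

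**2. Chance selections.** The threshold is assumed, as is independence of covariates unrelated to outcome.

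| Threshold | Expected of 18 | P(at least one) = 1 - (1 - threshold)^18 |
|---|---|---|
| 0.05 | 0.9 | 60% |
| 0.10 | 1.8 | 85% |
| 0.20 | 3.6 | 98% |

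Pairs among 18 covariates: 18 x 17 / 2 = 153, giving 153 x 0.05 = 7.7 chance findings. If treatment counts as a nineteenth term there are 171 pairs and 8.6 chance findings. The note does not say which is meant.

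**3. How far the estimate moves with ordinary baseline covariates.** Simulation: 500 patients at 1:1, about 51% events, true difference 0, 18 independent covariates, screen at p ≤ 0.05, standardised risk difference, 600 trials per setting (250 with interactions). Troponin was assumed 50% positive with odds ratio (OR) 1 to 5, because the documents give neither figure.

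| Troponin OR | Troponin selected | 95th-percentile shift, screened v unadjusted | SE with troponin fixed (0.0446 unadjusted) |
|---|---|---|---|
| 1 | 7% | 1.0 points | 0.0446 |
| 2 | 97% | 1.8 points | 0.0440 |
| 3 | 100% | 2.4 points | 0.0430 |
| 5 | 100% | 3.7 points | 0.0412 |

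The proportion of trials whose bound cleared 19.1 points stayed at 98% to 100%. Screening covariate-by-covariate interactions as well, at OR 3, let in 7.5 null terms on average. The 95th-percentile shift was then 3.2 points, and the mean printed SE fell from 0.0429 to 0.0415 with no real gain in information. Treatment-by-covariate terms were not simulated.

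**4. Total infusion time.** By design, short tirofiban runs for the procedure plus 1 to 2 hours; eptifibatide and long tirofiban run 12 to 18 hours after PCI. Assumed total hours: short 1.5 to 3.0; comparator 12.5 to 18.5; extended short infusions 12 to 18; each uniform. Protocol 5.2.4 extends short infusions after a thrombotic complication but gives no frequency, so 5% is assumed.

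- Short-arm mean = 0.95 x 2.25 + 0.05 x 15 = 2.89. Comparator mean = 15.5. Difference = 12.61.
- Variance between arms = 12.61² / 4 = 39.8.
- Short-arm variance = 0.95 x 0.1875 + 0.05 x 3 + 0.95 x 0.05 x 12.75² = 8.05. Comparator variance = 3. Mean within-arm variance = 5.52.
- Variance inflation = 1 + 39.8 / 5.52 = 8.2.
- SE = 0.0447 x √8.2 = 0.128. Chance of clearing the margin = Φ(0.191 / 0.128 - 1.96) = 32%.
- 95th-percentile shift = 1.96 x √(0.128² - 0.0447²) = 23 points.

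Simulation (400 trials) agrees: SE 0.045 to 0.125, pass rate 98% to 33%, shift 23 points. By the same formulas, other extension frequencies give:

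| Short infusions extended | SE | Pass rate |
|---|---|---|
| 0% | 0.239 | 12% |
| 5% | 0.128 | 32% |
| 10% | 0.100 | 48% |
| 20% | 0.077 | 71% |

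These figures apply once the variable is in the model. With no true treatment difference, the screen picked it in 6% of trials at p ≤ 0.05 and 15% at p ≤ 0.20. Averaged over all trials, the pass rates were 97% (99% unadjusted) and 90% (99% unadjusted). If the arms truly differ, infusion time stands in for arm and would pass the screen more often. In long tirofiban versus eptifibatide the planned durations match, so this collinearity does not arise.

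**The case against.** The strongest reply is that SAP 3.10.4 calls the analysis exploratory. A reader might infer from an adjusted model of the primary endpoint that the non-inferiority conclusion itself hangs on the screen. The documents do not support that: SAP 3.10.1 rests the claim on treatment alone.

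Counting chance selections also overstates the harm. The note offers terms for consideration, not automatic entry. The candidates are not independent: for example, three P2Y12 agents that are mutually contraindicated sit alongside three P2Y12 timing windows. Step 3 shows that ordinary baseline covariates move the estimate little. Part of that movement is legitimate correction of chance imbalance, which a fixed model would also make. That six different models would result is a possibility, not something the SAP states.

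A reader might also infer that leaving baseline troponin unforced throws away substantial precision. The documents give no prevalence of positive troponin and no strength of association, and a strong predictor would almost always pass the screen. At an assumed OR of 3 the gain is 1 - 0.0430 / 0.0446 = 4% in SE, for a test already powered at about 99%.

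All of this stands. It does not answer the missing selection rule, the post-randomisation candidates or the open-ended sentence in Protocol 9.6.

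**Conclusion.** The point holds for the exploratory adjusted analysis only. The confirmatory test is unaffected. As written, the adjusted estimate cannot be reproduced from the SAP, its interval ignores selection, and its covariates may differ between tables.

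For ordinary baseline covariates the consequence is small: shifts of about 1 to 4 points against 19.1, on the assumptions of step 3. The consequential fault is the admission of post-randomisation variables, above all total infusion time in the two comparisons that involve short tirofiban. If it enters, the SE rises by a factor of about 1.7 to 5 over an assumed 20% to 0% of extended infusions, and the adjusted estimate could appear to contradict a sound primary result. The case for fixing access and troponin rests on stratification and reproducibility; the gain in precision is modest. The change should be made, because it is cheap and uses data already collected.

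**What to change.** - In SAP 3.10.4 and the Table 15(a) note, delete the univariate screen and the interaction search.
- Remove every post-randomisation variable from the adjusted model: total infusion time, number of stents, number of vessels treated, and P2Y12 therapy in the window running to 15 minutes after PCI.
- Prespecify one logistic model for all three comparisons and both populations: treatment, planned access and baseline troponin (positive or negative, as already listed). Urgent or elective indication is optional, but decide before database lock.
- Report the standardised risk difference with its one-sided 97.5% bound, labelled supportive to SAP 3.10.1.
- Keep subgroup interactions as a separate display that does not feed the adjusted estimate.
- Limit the Protocol 9.6 sentence on adjustments to this prespecified model.

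The cost is SAP wording, one protocol sentence and simpler programming. No new data are needed. The small downside is that the sponsor gives up choosing covariates after seeing the data.

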4.1 Inclusion Criteria

- a. Age \geq 18 years of age

- b. Scheduled to undergo PCI with an FDA approved or cleared device (stent or procedures such as balloon angioplasty, rotablation, AngioSculpt, laser atherectomy, etc.) in one or more native coronary target lesions
- c. Written informed consent.

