4.2 Exclusion Criteria

- a. Primary PCI for STEMI as index procedure
- b. Prior STEMI within 48 hours before randomization
- c. Prior PCI within 30 days before randomization
- d. Planned staged PCI within the subsequent 48 hours after index PCI
- e. Planned PCI of vein graft lesions only
- f. Use of abciximab within 7 days before randomization
- g. Use of tirofiban or eptifibatide within 12 hours before randomization
- h. Use of low-molecular weight heparin within 12 hours before randomization
- i. Use of bivalirudin within 12 hours before randomization
- j. Use of warfarin within 7 days before randomization unless INR \leq 1.3
- k. Use of dabigatran or rivaroxaban within 3 days prior to randomization
- l. Use of thrombolytic agents administered within 24 hours before randomization
- m. Pregnant
- n. Active pericarditis
- o. Presumed or documented history of vasculitis
- p. Uncontrolled hypertension (blood pressure $>$ 180/110 mm Hg)
- q. Dependency on renal dialysis
- r. Active internal bleeding or bleeding diathesis, surgery, trauma or gastrointestinal/genitourinary tract bleeding within 6 weeks prior to randomization
- s. Prior intracranial hemorrhage, hemorrhagic stroke, cerebrovascular accident (CVA) within 2 years or CVA with significant residual neurological deficit, intracranial neoplasm, arteriovenous malformation, aneurysm, or structural abnormality
- t. Thrombocytopenia (platelet count $<$ 100 x 10³ μ L) or history of thrombocytopenia following heparin, tirofiban or eptifibatide
- u. Planned participation in any other clinical trial of an investigational drug or device, or a clinical trial of an approved drug or device for a non-approved use, up to 48 hours following PCI
- v. Participation in another clinical trial 30 days prior to participation in the current study
- w. Any other condition that in the opinion of the investigator may compromise the safety or compliance of the patient or would preclude patient successfully completing the trial
- x. Known inability to comply with the protocol for the duration of the study.

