9.3.4 Potential Covariates and/or Subgroups

- Patient with acute coronary syndromes
- STEMI > 48 hours
- Stable angina
- Troponin baseline negative
- Troponin baseline positive
- Femoral access PCI
- Radial access PCI
- Total stent length
- Use of a closure device
- Number of stents implanted
- Single vessel
- Multivessel
- Number of vessels treated
- Total infusion time

- Patients receiving P2Y₁₂ antagonist therapy between 24 and 6 hours prior to randomization
- Patients receiving P2Y₁₂ antagonist therapy between 6 and 1 hours prior to randomization
- Patients receiving P2Y₁₂ antagonist therapy between 1 hour prior to randomization and 15 minutes after completion of the PCI procedure
- Type 1 diabetes mellitus
- Type 2 diabetes mellitus
- Prior use of GPIIb/IIIa inhibitor therapy
- Indication for PCI
- Age < 65 years, ≥65 years and ≥75 years
- Sex
- Race
- Clopidogrel
- Prasugrel
- Ticagrelor
- Elective PCI
- Urgent PCI

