Femoral			
Radial			
Number of stents implanted			

Parameter	Treatment Group		
	Short Tirofiban (N=)	Eptifibatide (N=)	Long Tirofiban (N=)
Available n			
Mean ± SD			
95% CI for Mean			
Median (IQR)			
Min - Max			
Vessel involvement, n (%) ²			
Single Vessel			
Multivessel			
Patients receiving P2Y12 antagonist therapy between 24 and 6 hours prior to randomization, n (%)			
Yes			
No			
Patients receiving P2Y12 antagonist therapy between 6 and 1 hours prior to randomization, n (%)			
Yes			
No			
Patients receiving P2Y12 antagonist therapy between 1 hour prior to randomization and 15 minutes after completion of the PCI procedure, n (%)			
Yes			
No			
Type 2 diabetes mellitus, n (%)			
Yes			
No			
Indication for PCI, n (%)			

Parameter	Treatment Group		
	Short Tirofiban (N=)	Eptifibatide (N=)	Long Tirofiban (N=)
Elective			
Urgent			

¹ Defined as any previous diagnosis of unstable angina, NSTEMI or STEMI

² Ascertained by 'Number if stents implanted' indicated on the Procedure Report Form; ≥ 1 implanted stent = multivessel

Note: This table will also be repeated for Per-Protocol Population.

Table 14. Descriptive Statistics of Primary Outcome by Treatment Group – mITT Population

Parameter	Treatment Group		
	Short Tirofiban (N=)	Eptifibatide (N=)	Long Tirofiban (N=)
Primary outcome, n (%)			
Yes			
No			
Death, n (%)			
Yes			
No			
Periprocedural myonecrosis (PPM), n (%)			
Yes			
No			
Urgent target vessel revascularization (uTVR), n (%)			
Yes			
No			
REPLACE-2 major bleeding, n (%)			
Yes			
No			

Note: The primary outcome is the composite of death, PPM, uTVR or REPLACE-2 major bleeding within 48 hours following PCI or hospital discharge, whichever comes first.

Note: This table will also be repeated for Per-Protocol Population.

Table 15. Bivariate Logistic Regression Model for Primary Outcome – mITT Population

Parameter	Level	Estimate	Standard Error (SE)	Odds Ratio (OR)	95% CI for OR	Risk (Proportion Difference)	Standard Error (SE) of Risk Difference	95% CI for Risk Difference	p-value *
Primary composite outcome	Short Tirofiban vs. Eptifibatide								
Primary composite outcome	Short Tirofiban vs. Long Tirofiban								
Primary composite outcome	Long Tirofiban vs. Eptifibatide								

* p-value is the overall p-value from the logistic regression model.

Note: The primary outcome is the composite of death, PPM, uTVR or REPLACE-2 major bleeding within 48 hours following PCI or hospital discharge, whichever comes first.

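### The SAP's acute coronary syndrome covariate is defined by any past diagnosis, so it mixes lifetime history with index presentation

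*SAP*

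**What the plan says.** Protocol section 9.3.4 lists "Patient with acute coronary syndromes" among the potential covariates and subgroups, without a definition. The SAP supplies one. In section 3.10.4 the item reads "Patient with acute coronary syndromes (defined as any previous diagnosis of unstable angina, NSTEMI or STEMI". Footnote 1 of mock Table 13 repeats it: "Defined as any previous diagnosis of unstable angina, NSTEMI or STEMI". Because the rule appears in both the methods text and the table shell, it is the working derivation rule and not a slip of wording.

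The same SAP list carries, as separate items, stable angina, STEMI more than 48 hours old, baseline troponin (positive or negative), and "Indication for PCI (Urgent vs. Elective".

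The two documents give the covariate different roles:

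- SAP 3.10.4 describes screening for model entry: "As an exploratory analysis, appropriate univariate statistics will be used to identify potential confounders for inclusion in multivariable regression models". Mock Table 15(a) extends the screening to significant two-way interaction terms.
- Protocol section 9.6 plans formal subgroup analyses through interaction terms in logistic models and refers to the list in 9.3.4 for the covariates.

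The primary comparison in SAP 3.10.1 has treatment group as its only independent factor.

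**The concern.** The label describes a patient who has an acute coronary syndrome. The rule asks whether the patient has ever had one. These differ in a trial that enrols both acute and stable patients. A man with an NSTEMI ten years ago who now has elective PCI for stable angina satisfies the rule.

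Three outputs are affected. The ACS row of Table 13 would count patients with a history of ACS under a heading that reads as presentation. The ACS term offered to the exploratory models of Table 15(a) would adjust for a mixture. The protocol's ACS subgroup or interaction analysis would split patients on that mixture, so a difference in treatment effect between acute and stable presenters would tend to look smaller than it is. Presentation plausibly matters here because the composite includes periprocedural myonecrosis, which is judged against baseline troponin.

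**Working it through.** **Step 1. Can a stable patient with an old infarct enter the trial?** Inclusion (protocol 4.1) requires a patient "Scheduled to undergo PCI with an FDA approved or cleared device" in a native coronary lesion and does not require an acute presentation. The exclusions that concern STEMI (protocol 4.2) are "Primary PCI for STEMI as index procedure" and "Prior STEMI within 48 hours before randomization". Every STEMI that can count towards the flag is therefore more than 48 hours old, with no upper limit on its age. No exclusion refers to an earlier NSTEMI or unstable angina. So the answer is yes.

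**Step 2. How is that patient coded?** Take a stable elective patient with a remote infarct.

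| SAP item | Code |
|---|---|
| ACS (any previous diagnosis) | Yes |
| Stable angina | Yes |
| Indication for PCI | Elective |

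Nothing in SAP 3.10.4 makes the first two exclusive, so all three codes can hold together.

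**Step 3. How much mixing could there be?** Neither document gives a figure that depends on the flag, so there is nothing of the plan's own to reproduce, and no sample size or power calculation uses it. The following is an illustration on assumed values. Let q be the share of patients who present with ACS, all of them flagged. Let h be the share of the remaining patients who have an old ACS diagnosis.

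- Share flagged = q + (1 − q)h
- Share of flagged patients who truly present with ACS = q / [q + (1 − q)h]

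With q = 0.40:

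- h = 0.2: flagged = 0.40 + 0.12 = 0.52; not presenting with ACS = 0.12/0.52 = 23%.
- h = 0.5: flagged = 0.40 + 0.30 = 0.70; not presenting with ACS = 0.30/0.70 = 43%.

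Over a wider range, the share of flagged patients who truly present with ACS is:

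| | h = 0.1 | h = 0.3 | h = 0.5 |
|---|---|---|---|
| q = 0.2 | 0.20/0.28 = 71% | 0.20/0.44 = 45% | 0.20/0.60 = 33% |
| q = 0.4 | 0.40/0.46 = 87% | 0.40/0.58 = 69% | 0.40/0.70 = 57% |

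**Step 4. What does this do to an ACS contrast?** Write P for the share in the table. Let D₁ be a quantity (event rate or treatment risk difference) in patients presenting with ACS, and D₀ the same quantity in the others. Suppose old history does not itself change the outcome. The flagged group then averages P·D₁ + (1 − P)·D₀, and the unflagged group has D₀. The observed contrast is P(D₁ − D₀), so the fraction of the true contrast that survives equals P. This is exact on the risk-difference scale. If old ACS history does affect outcome, the size and direction of the distortion are not determined.

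**The case against.** The strongest reply is that little depends on this flag. The primary test does not use it. The SAP calls the covariate work exploratory, and ACS is one of 18 listed candidates that may never enter a model. In a randomised comparison, a poorly coded baseline covariate does not in itself bias the treatment effect. Table 13 prints the definition in its footnote, so a careful reader can see what was counted. All of this stands, and it limits the weight of the point. It does not make the rule measure what its label says.

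Some stronger readings are tempting but not supported:

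- *That results in ACS patients could not be read from the trial at all.* Stable angina, baseline troponin, STEMI more than 48 hours old and urgent versus elective PCI are tabulated and capture presentation in part, although they do not isolate unstable angina.
- *That the demographic and baseline table is wrong.* Table 3 has no ACS row; the mislabelling is confined to Table 13.
- *That a first-ever ACS prompting the index PCI would be coded No because it is not previous.* Under protocol 5.2.2, randomisation follows a final decision to proceed to PCI, so that diagnosis would ordinarily already have been made. The wording could be clearer, but this reading is strained, and nothing above relies on it.
- *That the protocol sets ACS against stable angina and elective PCI as alternative presentations.* Section 9.3.4 is a flat list with no definitions. The case rests on the plain meaning of the label and on the SAP's own rule.

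**Conclusion.** The point holds as a defect in a named covariate. As written, the SAP codes stable elective patients with an old ACS diagnosis as ACS patients, and the flag pools history with presentation. The consequences are a mislabelled row in Table 13, a blurred term in the exploratory models, and a blurred split in the protocol's ACS subgroup or interaction analysis.

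The size depends on prevalences that the documents do not give. Over the assumed ranges (20% or 40% presenting with ACS; 10% to 50% of the rest with old history), 33% to 87% of flagged patients would truly present with ACS. The ACS contrast would shrink to that same fraction, provided that every current ACS is flagged and that old history does not itself affect outcome.

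The primary non-inferiority conclusion, the sample size and the error rate do not change. The correction should still be made before analysis, because choosing the definition after results are seen in an open-label trial would invite doubt about the choice.

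**What to change.** In SAP 3.10.4 and Table 13 footnote 1, define ACS by index presentation: unstable angina, NSTEMI, or STEMI more than 48 hours old, as the reason for the index PCI or diagnosed during the index admission. Make it mutually exclusive with stable angina as the index presentation. Keep any prior ACS as a separate medical-history variable, and use the redefined variable in Table 15(a) and in the protocol's subgroup analysis.

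First confirm that the CRF holds the index diagnosis. The documents do not show this: protocol 5.2.1 asks for a brief medical history, SAP 3.6 codes history by organ class and preferred term without mentioning dates, and the SAP reduces the indication for PCI to urgent or elective. If the field is missing, relabel the existing variable as history of ACS (any prior) and do not report it as an ACS-presentation subgroup.

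The cost is a small change to SAP text and derivation code, subject to that check. If the field is missing, only the label and the reporting change.
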